With implementation of protocol Amendment 5, participants who were initially enrolled to receive placebo (Groups 6, 8 and 10), will be offered a 2-dose (28-day interval) Ad26.COV2.S vaccination regimen at the 5x10¹⁰ vp dose level. In October 2020, the study was temporarily paused because one of the pausing rules was met in study COV3001. When the pause was lifted, most of the participants in Groups 7-8 had missed their visit window for Vaccination 2 (Visit 4), rendering the

intent of the 28-day vaccination interval in these groups futile. The goal in offering 2 doses of study vaccine to those participants who initially received placebo in this study is to recreate this 28-day vaccination interval, and to restore the objectives associated with this interval. The original 28-day interval target group was 75 participants. Hence the total number of placebo recipients from Groups 6, 8 and 10 (target n 75) is intended to fulfill the original target enrollment for Group 7.

With implementation of protocol Amendment 5, all adult participants will be unblinded to the primary vaccination regimen, and, adults who received placebo in the primary vaccine regimen, will receive a 2 dose active Ad26.COV2.S vaccine regimen at a 28-day interval and at a dose level of $5x10^{10}$ vp, in an open-label manner. Per group, approximately one third of participants will be 65 years and older.

Adult participants who received the active vaccine in the primary vaccine regimen will be followed up for 12 months after vaccination 2; adult participants who received placebo in the primary vaccine regimen will be followed up for 6 months after receipt of the unblinded vaccination 1 (ie, receipt of the first active vaccine following unblinding).

Groups 1-6

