400 participants (75 participants per active vaccine group, 25 in the placebo group) will be randomized in parallel in a 3:3:3:3:1 ratio to 1 of 6 vaccination groups. Participants will receive a 2-dose (56-day interval, Groups 1-3) vaccination regimen at different dose levels (5×10^{10} vp, 2.5×10^{10} vp, and 1.25×10^{10} vp) or single-dose vaccination regimen (Groups 4-5) at different dose levels (1×10^{11} vp, 5×10^{10} vp), or placebo (Group 6). For blinding purposes, participants in the single-dose groups (Groups 4-5) will receive a placebo vaccination on Day 57. Additional exploratory cellular immunogenicity evaluations (PBMC) will be performed in a subset of participants (21/group in Groups 1-5, 7 in Group 6; at selected sites). Participants in Group 6 who received 2-doses of placebo in the primary vaccine regimen will receive 2 doses of active vaccine at a single dose level of 5×10^{10} vp, at a 28-day interval.

Groups 7-8

75 participants (50 participants in the active vaccine group, 25 in the placebo group) will be randomized in parallel in a 2:1 ratio, to 1 of 2 vaccination groups. Participants will receive a 2 dose (28-day interval, Groups 7^a) vaccination regimen at a 5×10^{10} vp dose level or placebo (Group 8). Participants in Group 8 who received 2-doses of placebo in the primary vaccine regimen will receive 2 doses of active vaccine at a single dose level of 5×10^{10} vp, at a 28-day interval.

-

^a Group 7 and 8: only 2 subjects (one in each group) are vaccinated at a 28-day interval, due to a study pause

Groups 9-10

75 participants (50 participants in the active vaccine group, 25 in the placebo group) will be randomized in parallel in a 2:1 ratio, to 1 of 2 vaccination groups. Participants will receive a 2 dose (84-day interval, Group 9) vaccination regimen at a 5×10^{10} vp dose level or placebo (Group 10). Participants in Group 10 who received 2-doses of placebo in the primary vaccine regimen will receive 2 doses of active vaccine at a single dose level of 5×10^{10} vp, at a 28-day interval.

The vaccination schedules are presented in Table 2.

Table 2: Vaccination Schedules Adults

Adults ≥18 to ≤55 Years and ≥65 Years

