6.3. Measures to Minimize Bias: Randomization and Blinding

Vaccine Allocation

Procedures for Randomization and Stratification

Central randomization will be implemented in this study. Participants will be randomly assigned to 1 of the vaccine groups based on a computer-generated randomization schedule prepared before the study by or under the supervision of the sponsor. For adults, the randomization will be balanced by using randomly permuted blocks and will be stratified by study site and age group (approximately two thirds of participants $\geq 18-\leq 55$ years of age and one third of participants ≥ 65 years of age per group). For the adolescent cohort, the randomization will be balanced by using randomly permuted blocks and will be stratified age group (half of participants 12 to 15 years of age inclusive and half of participants 16 to 17 years of age inclusive per group).

From the time of protocol Amendment 2, for each of the age strata (16 to 17 years and 12 to 15 years) in the adolescent cohort, the safety of the Ad26.COV2.S vaccine at a dose level of 2.5×10^{10} vp (Group A-C) or 5×10^{10} vp (Group D-F) was planned to be evaluated by dose escalation in a sequential manner initially in groups of sentinels (11 participants in each group) and subsequently if the safety profile is favorable, in a group of 22 participants that will form the safety cohort (randomization ratio of 5:5:1 for both sentinels and safety cohorts). Safety was to initially be assessed in older adolescents (16 to 17 years of age) before proceeding with evaluation of safety in cohorts of younger adolescents (12 to 15 years of age). If, the safety profile is found to be acceptable, enrollment of study participants in Groups D-F was to start.

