5.7.1.5. Immunogenicity against the insert

5.7.1.5.1. Humoral assays

For VNA (both wild-type virus and pseudovirion expressing S protein, as available), the following statistics will be calculated: N, geometric mean and corresponding 95% CI of the actual values, fold increase from baseline, fold increase from pre-dose 2 (for time points after dose 2), fold increase from pre-antigen presentation (for time points after the antigen presentation), difference to Ad26 5e10: GMR (95% CI) for Geometric mean and GMR (95% CI) for Geometric mean increase from Baseline.

For the calculation of the geometric mean and its corresponding 95% CI, the arithmetic mean and its corresponding 95% CI are calculated on the \log_{10} transformed values. These values are back transformed to provide the geometric mean and its corresponding 95% CI.

For wild-type and pseudovirion VNA separately:

- A sample will be considered positive if the value is strictly greater than the LLOQ (>LLOQ).
- Responder definition. A post-baseline sample will be considered a responder if at least one of the following conditions is satisfied:
 - The baseline sample value is less than or equal to the LLOQ (\leq LLOQ) and the post-baseline sample value is strictly greater than the LLOQ (>LLOQ)
 - The baseline sample value is strictly greater than the LLOQ (>LLOQ) and the post-baseline value represents an at least 4-fold (\geq 4-fold) increase from the baseline sample value.

Actual values are tabulated and shown as dot plots with dots for participant values, and the corresponding geometric mean and 95% CI per time point for each assay. In addition, GMT plots over time, combining the regimens in one graph (without individual participant dots) will also be generated.

Participant profiles of the actual values over time will be graphically presented.

Reverse distribution curves of the actual values are provided for selected time points.

In the graphs, original values will be displayed on the \log_{10} scale.

Further details and/or updated rules will be provided in the DPS.

For **S-ELISA**, the same as above applies.

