5.7.1.6.1. Dose response modeling

To explore the dose effect of single vaccination, data from D14 post 1st Vaccination of the groups 1-10 will be analyzed using a regression model with log10 transformed VNA and ELISA results as dependent variable and dose as exploratory variable. Depending on the pattern observed a linear or non-linear model will be used.

To explore the dose effect of single vaccination, data from D28 post 1st Vaccination of the groups 1-10 will be analyzed using a regression model with log10 transformed VNA and ELISA results as dependent variable and dose as exploratory variable. Depending on the pattern observed a linear or non-linear model will be used.

To explore the dose effect of the 56day double vaccination regimen, data from D28 post 2nd Vaccination of the groups 1:3, and 6 will be analyzed using a regression model with log10 transformed VNA and ELISA results as dependent variable and dose as exploratory variable. Depending on the pattern observed a linear or non-linear model will be used.

To explore the dose effect of the 56day single vaccination regimen, data from D28 post 2nd Vaccination of the groups 4:5, and 6 will be analyzed using a regression model with log10 transformed VNA and ELISA results as dependent variable and dose as exploratory variable. Depending on the pattern observed a linear or non-linear model will be used.

Depending on the observed data pattern, the placebo groups may be excluded from the analysis and focus set only on the dose response relationship within the active doses studied.

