5.7.1.6.2. Interval response modeling

To explore the interval duration effect of the double vaccination regimen, data from D28 post 2nd Vaccination of the groups 3, 7 and 9 will be analyzed using a regression model with log10 transformed VNA and ELISA results as dependent variable and interval duration as exploratory variable. Depending on the pattern observed a linear or non-linear model will be used.

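### Adult randomisation is stratified by age group, but the SAP's dose and interval models and its overall GMR carry no age term, so their intervals may be slightly too wide

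*SAP*

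**What the plan says.** Protocol 6.3 states that for adults "the randomization will be balanced by using randomly permuted blocks and will be stratified by study site and age group". It sets about two thirds aged 18-55 and one third aged ≥65 in each group, and Protocol 4.1 repeats: "Per group, approximately one third of participants will be 65 years and older".

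The planned estimates do not use that factor:

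- **Dose models.** All four in SAP 5.7.1.6.1 take the form "regression model with log10 transformed VNA and ELISA results as dependent variable and dose as exploratory variable". Protocol 9.2.1 likewise names dose as the only regressor.
- **Interval model.** SAP 5.7.1.6.2 has "interval duration as exploratory variable" and nothing else on the right-hand side.
- **GMR.** SAP 5.7.1.5.1 lists "difference to Ad26 5e10: GMR (95% CI) for Geometric mean", with no model or adjustment, and leaves further details to the data presentation specifications (DPS).
- **Site.** SAP 5.1.3 pools the centres.

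Age does appear elsewhere. SAP 5.7.1 asks for immunogenicity results by vaccine group and also by vaccine group within age group, and 5.7.4 plans selected analyses by age group. SAP 5.7.1.6 describes the modelling as exploratory and unpowered. Protocol 9.2.1 and SAP 5.3.1, however, make the dose-response and interval-response relationships the primary immunogenicity objective in adults.

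**The concern.** Stratifying by age takes the age component out of the true sampling error of a between-arm contrast. A model without age puts it back into the residual variance, so the reported interval is wider than the design delivers. The by-age tables do not cure this: they split the sample and never recombine it into one adjusted estimate. Since the study tests no hypothesis, the estimates and their intervals are the result, so their width matters even without a decision rule.

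The second stake is protection against imbalance. If the age mix drifts apart between the sets compared, an unadjusted contrast carries the age effect with it. An age term fixed in advance guards against that and avoids a choice made after seeing the data.

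**Working it through.** **1. What the plan supplies.** No SD, age effect or interval width is given for log10 titres. The only precision figure is Protocol Table 9, for zero events. It reproduces from 1 − 0.05^(1/N): 11.29%, 5.82%, 3.92% and 1.98% for N = 25, 50, 75 and 150, against the printed 11.3%, 5.8%, 3.9% and 2.0%. It says nothing about titres, so the rest uses assumptions.

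**2. Inputs.** From the protocol: 75 per active arm in Groups 1-5, and share aged ≥65 p = 1/3. Assumed: within-stratum SD s = 0.4-0.6 log10, and titres lower by d = 0.1-0.3 log10 at ≥65.

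**3. Excess width at balanced age.** Omitting age adds p(1 − p)d² = (2/9)d² to the residual variance, so the width ratio is √(1 + (2/9)(d/s)²). Excess log10 interval width:

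| | d = 0.1 | d = 0.2 | d = 0.3 |
|---|---|---|---|
| s = 0.4 | 0.7% | 2.7% | 6.1% |
| s = 0.5 | 0.4% | 1.8% | 3.9% |
| s = 0.6 | 0.3% | 1.2% | 2.7% |

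With d = 0 the excess is 0. With s as low as 0.3 and d = 0.3 it would be 10.6%.

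**4. As sample size.** The equivalent share discarded is 1 − 1/(variance ratio). At s = 0.4, d = 0.3 the variance ratio is 1 + (2/9)(0.75)² = 1.125, giving 1 − 1/1.125 = 11.1%. At s = 0.6, d = 0.1 it is 1.0062, giving 0.6%.

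**5. On the GMR scale.** For 75 vs 75 with s = 0.5, the adjusted factor is 10^(1.96 × 0.5 × √(2/75)) = 1.446. With d = 0.2 the unadjusted factor is 1.455.

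**6. Simulation check (20,000 runs, age balanced, s = 0.5, d = 0.3).**

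| | Unadjusted mean SE | Actual SD of estimate | Unadjusted coverage |
|---|---|---|---|
| 75 vs 75 | 0.0848 | 0.0815 | 95.9% |
| Dose slope, Groups 1-3 | 0.0222 | 0.0214 | 95.8% |

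Adding age brings the mean SE to 0.0815 and 0.0214. The estimate itself is no noisier without the age term; only the stated interval is too wide.

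**7. By-age tables.** A 75-person arm splits into about 50 and 25. At s = 0.5 the separate GMR factors are 10^(1.96 × 0.5 × √(2/50)) = 1.57 and 10^(1.96 × 0.5 × √(2/25)) = 1.89. Neither replaces a combined estimate at 1.446.

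**8. Bias.** On the log10 scale it equals −(difference in share ≥65) × d. At the planned mix the difference is zero, so the bias is zero. As an illustration only, 38/75 against 25/75 aged ≥65 with d = 0.3 gives −(13/75) × 0.3 = −0.052, a GMR factor of 0.89. Simulated coverage at s = 0.5 is then 91.9% unadjusted and 95.1% adjusted. With d = 0.1 the bias is −0.017 and unadjusted coverage is 94.7%.

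**The case against.** The strongest reply is that this is a small, conservative inefficiency in models the SAP itself calls exploratory. No margin, test or success rule depends on them, and the size rests on an SD and an age effect that the documents do not give. That stands as a limit on importance. It does not remove the point, because these models serve the primary immunogenicity objective and the improvement is nearly free.

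A reader might infer that the GMRs ignore age altogether. The documents do not support that: SAP 5.7.1 requires results within age group, and the GMR statistics fall under that instruction. Nor does the SAP state an unadjusted method for the GMR interval. It gives a calculation for the geometric mean only and defers details to the DPS. What is missing is a specified age-adjusted overall GMR.

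A further objection concerns models that include placebo. Values below the LLOQ are set to LLOQ/2 for geometric means (SAP 5.7.1.2), so placebo values may sit at a floor where a common age shift is implausible. This is fair, and it shapes the fix.

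**Conclusion.** The omission is clear from the text. Its cost in precision is small: 0.3% to 6.1% of interval width, or 0.6% to 11.1% of the sample, under the assumed SD and age effect, and nothing if age does not predict titre.

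A reader might go further and infer that the planned contrasts are biased. The documents do not support this. About one third aged ≥65 is planned in every group, including the separately allocated Groups 7-8 and 9-10, and bias at that mix is zero. Bias needs an age effect and an imbalance together. Imbalance is plausible but not shown in three places:

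- the modified PPI and FAS sets, which move Group 7-8 participants into Groups 1 and 6 (SAP Appendix 2);
- the PPI after exclusions (SAP 4);
- any later contrast with the open-label former placebo recipients meant to restore the 28-day interval (Protocol 4.1). Neither SAP modelling section names that cross-vaccinated regimen, and no age shares for it are given.

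An age term does not repair a separate contradiction. SAP 5.7.1.6.2 combines Group 3, listed at 1.25×10^10 vp in Protocol Table 2, with Groups 7 and 9, listed at 5×10^10 vp, so interval is confounded with dose. Appendix 2 also removes Groups 7-8 from the PPI. These passages must be reconciled.

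**What to change.** - **SAP 5.7.1.6.1 and 5.7.1.6.2:** add age group (18-55 / ≥65) as a fixed factor to the dose and interval models. Where a model includes placebo, also report the fit on active doses only.
- **SAP 5.7.1.5.1:** take the overall GMR and its 95% CI from a linear model on log10 titre with arm and age group. Keep the unadjusted GMTs and the by-age tables.
- **Cross-vaccinated cohort:** label any contrast with it as non-randomised and report it age-adjusted.
- **Site:** this is the other stratification factor. A site term is optional, if numbers per site allow.

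The cost is a few SAP lines and one degree of freedom per model. Age group is already in the randomisation data. Reconciling the groups, doses and analysis sets in 5.7.1.6.2 with Protocol Table 2 and SAP Appendix 2 is a separate correction.

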9.2.1. Immunogenicity

The primary objective in the adult population of the study is to explore the dose-response and interval-response relationship of humoral immune responses induced by different dose levels and different vaccine administration timings of Ad26.COV2.S using VNA titers and ELISA U/mL.

To explore the dose-response relationship between VNA/ELISA and different dose levels of the Ad26.COV2.S vaccine, a separate linear regression model will be fitted for:

- all active groups 14 days post vaccination 1
- all active groups 28 days post vaccination 1
- the 2-dose active groups using data of Groups 1-3, 28 days post vaccination 2
- the single-dose active groups using data of Groups 4-5, 28 days post vaccination 2
- the 2-dose active groups, using data of groups 1-3, 14 days post vaccination 2

In the linear regression model the log transformed VNA/ELISA titers at each timepoint will be used as dependent variable and the dose levels as independent variable.

Depending on the model fit, other models (eg, log-linear models or EMAX models) may be explored as well for the 56-day interval regimen.

Details on the comparison between the different dose levels and vaccination interval groups will be outlined in the SAP.

9.2.2. **Safety**

Placebo recipients are included for blinding and safety purposes and will provide additional control specimens for the immunogenicity assays.

While mild to moderate vaccine reactions (local site and systemic responses) are expected, AEs that preclude further dose administration or more serious ones that would limit product development are not anticipated. The observation of 0 events (eg, SAEs) is associated with 95% confidence that the true event rate is below the rates specified in Table 9 for the considered number of participants.

Table 9: Upper Limit of the 95% One-sided Confidence Interval if no Cases are Observed for Different Sample Sizes

Sample Size	N=25	N=50	N=75	N=150
Upper Limit 95% one- sided CI	11.3%	5.8%	3.9%	2.0%

CI = confidence interval, N = number of participants

Table 10 provides the probability of observing at least one AE in a group of the considered sample size given several true AE rates.

True AE Rate	Probability of Observing at Least One AE in N Participants (%)				
(%)	N=25	N=50	N=75	N=150	
0.5	12	22	31	53	
1	22	39	53	78	
2.5	47	72	85	98	
10	93	99	>99.9	>99.9	
25	>99.9	>99.9	>99.9	>99.9	
50	>99.9	>99.9	>99.9	>99.9	

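### SAP dose-response models add placebo to the protocol's active-only regressions, set no rule for dropping it or for choosing the model form, leave one planned model undefined, and record none of this in Appendix 2

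*SAP*

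**What the plan says.** Protocol 9.2.1 states that "a separate linear regression model will be fitted for" five data sets. They are all active groups 14 days after vaccination 1; "all active groups 28 days post vaccination 1"; Groups 1-3 at 28 days after vaccination 2; "the single-dose active groups using data of Groups 4-5, 28 days post vaccination 2"; and "the 2-dose active groups, using data of groups 1-3, 14 days post vaccination 2". On model form it adds that, subject to fit, "other models (eg, log-linear models or EMAX models) may be explored as well for the 56-day interval regimen".

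SAP 5.7.1.6.1 has four model paragraphs. In one, "data from D28 post 1st Vaccination of the groups 1-10 will be analyzed using a regression model with log10 transformed VNA and ELISA results"; another uses the same groups at 14 days after the first dose. The other two are at 28 days after vaccination 2: Groups 1-3 with Group 6, and Groups 4-5 with Group 6. Protocol Table 2 shows Groups 6, 8 and 10 as placebo. Each paragraph ends "Depending on the pattern observed a linear or non-linear model will be used". The section closes with "Depending on the observed data pattern, the placebo groups may be excluded from the analysis".

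SAP 5.7.1.6 names 14 and 28 days after both vaccinations as dose-response time points. SAP 5.3.1 gives these regressions as the way to explore the primary immunogenicity objective in adults. Appendix 2, the log of changes to protocol-planned analyses, covers only the October 2020 pause and Groups 7-8.

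**The concern.** Protocol 2.1 and 4.3 give the purpose of the lower doses: dose sparing and possible bridging to a lower-dose regimen. The question is how active doses compare with each other. Placebo answers a different one, vaccine versus none. If both enter one straight line, a step between placebo and vaccine is read as a gradient across doses.

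Two choices also follow the data without a rule: placebo in or out, and linear or non-linear. That gives at least 2 x 2 = 4 possible fits per model, since the non-linear form is not named. A reported slope would then have a meaning fixed only after the data were seen, and it could disagree with the geometric mean ratios in the same report.

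**Working it through.** The documents give no effect size, SD or power for these models, so there is no plan figure to reproduce. Planned group sizes (Protocol 4.1) are 75 in each of Groups 1-5, 50 in Groups 7 and 9, and 25 in Groups 6, 8 and 10: 475 active + 75 placebo = 550, the stated adult target.

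**Step 1: the models side by side (planned maximum N; dose levels in brackets)**

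| Time point | Protocol 9.2.1 | SAP 5.7.1.6.1 |
|---|---|---|
| D14 post 1 | 375 (4) | 400 (5) |
| D28 post 1 | 475 (4) | 550 (5) |
| D28 post 2, Groups 1-3 | 225 (3) | 250 (4) |
| D28 post 2, Groups 4-5 | 150 (2) | 175 (3) |
| D14 post 2, Groups 1-3 | 225 (3) | no model |

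The D14 post 1 row counts Groups 1-6 only, because the schedules for Groups 7-10 have no Day 15 visit.

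**Step 2: slope produced by placebo alone**

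Suppose every active dose has the same mean, d log10 above placebo, and placebo is coded as dose 0. With n0 placebo participants out of N and dose x in 1e10 vp:

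slope = d x [Σnx x n0/N] / [Σnx² − (Σnx)²/N]

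Groups 1-6: Σnx = 75 x 23.75 = 1781.25 and Σnx² = 75 x 157.8125 = 11835.94. The numerator is 1781.25 x 25/400 = 111.33. The denominator is 11835.94 − 1781.25²/400 = 3903.81. The slope is 0.0285d. The active-only slope is 0.

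Spurious fold rise = 10^(slope x dose gap). The values of d are assumptions.

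| Data | Slope per d | Comparison (gap) | d | Fold |
|---|---|---|---|---|
| Groups 1-6, post 1 | 0.0285 | 2.5e10 to 1e11 (7.5) | 0.6; 1.2 | 1.34; 1.81 |
| Groups 1-6 plus 9-10, D28 post 1 | 0.0486 | 2.5e10 to 1e11 (7.5) | 0.6; 1.2 | 1.65; 2.74 |
| Groups 1-3 and 6, post 2 | 0.0889 | 1.25e10 to 5e10 (3.75) | 0.9; 1.5 | 2.00; 3.16 |
| Groups 4-5 and 6, post 2 | 0.0750 | 5e10 to 1e11 (5) | 0.6; 1.2 | 1.68; 2.82 |

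**Step 3: would it look convincing, and could a rule catch it?**

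Simulation used 4,000 trials per scenario, active SD 0.4 or 0.5, and placebo SD 0, 0.1 or equal to the active SD (all assumed). The lowest share of trials with the 95% CI for the slope above 0 was 54%, 97%, 99% and 98% in the order of the table. Active-only fits excluded 0 in 4%-6%. A 5% lack-of-fit F test rejected the straight line with placebo in 95%-100%.

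**Step 4: age group**

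Age is a randomisation stratum (Protocol 6.3), with about one third aged 65 or older. Leaving out an age effect δ widens intervals by the factor √(1 + (1/3)(2/3)δ²/SD²). This is 1.004 at δ = 0.1, SD 0.5, and 1.106 at δ = 0.4, SD 0.4. There is no bias.

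**The case against.** **The protocol already allows fit-driven forms.** It does, without a criterion, for the 56-day schedule. Groups 1-6 follow that schedule, and only they have a Day 15 visit, so for three of the four SAP models the freedom of form is arguably not new. It is clearly new for the D28 post-vaccination-1 model. The protocol offers other forms in addition to the linear fit; the SAP offers them as a replacement.

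**Placebo can be useful.** An Emax model normally needs a zero-dose anchor, and with two active levels in Groups 4-5 curvature cannot be judged without one. That supports a labelled additional fit, not an unrecorded change of the main data set.

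**The SAP permits the right analysis.** A reader might infer that it directs a misleading slope. It does not: it allows an active-only or non-linear fit and does not state how placebo is coded. The high rejection rate of the lack-of-fit test also suggests that inspection would often lead away from the straight line. What is missing is the rule.

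**The time point is not abandoned.** A reader might infer that the 14-day post-vaccination-2 analysis was withdrawn. SAP 5.7.1.6 still names it; only its model paragraph is absent.

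**Detail may sit elsewhere.** Protocol 9.2.1 leaves details of dose and interval comparisons to the SAP, and output detail goes to presentation specifications not available here. That does not cover a change to groups the protocol itself lists.

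**Conclusion.** The mismatch with Protocol 9.2.1 is real on all its parts, and Appendix 2 should have shown it. The consequence is conditional. Only if a straight line with placebo at dose 0 were kept would equal active responses give the fold rises in the working: about 1.3 to 1.8 for Groups 1-6 after dose 1 (1.6 to 2.7 if Groups 9-10 contribute Day 29 samples), 2.0 to 3.2 for Groups 1-3 and 6, and 1.7 to 2.8 for Groups 4-5 and 6. The flat active response, differences, SDs and dose-0 coding are assumptions.

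A reader might apply the same formula to all of Groups 1-10 at planned N (slope 0.0638d) and report 1.9- to 3.8-fold. That does not apply to the per-protocol immunogenicity set, from which Appendix 2 removes Groups 7-8. Nor is there an inflated error rate or a compromised primary test: no hypothesis is tested, SAP 5.7.1.6 calls the modelling exploratory, the listed primary endpoints are serological response and GMT/GMC, and SAP 5.7.1.5.1 plans geometric mean ratios against 5e10. Severity is low, but the correction is worth making because SAP 5.3.1 ties these regressions to the primary objective.

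**What to change.** Amend SAP 5.7.1.6.1 and Appendix 2:

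1. Make the active-only fit of Protocol 9.2.1 the main analysis. Keep it linear unless a lack-of-fit F test against group means rejects at 5%. In that case report the active group means and their contrasts with 95% CIs, or one Emax form named in advance. Label any fit that includes placebo as a sensitivity analysis, with an E0/Emax or on/off term.
2. For Groups 4-5, with two active levels, use the already planned geometric mean ratio of 1e11 to 5e10 in place of a slope.
3. Add the Groups 1-3 model at 14 days after vaccination 2, or record its removal.
4. Include the randomisation age group (18-55; 65 and over) as a covariate. This is a precision gain only: without it, intervals are about 0.4%-11% wider for an assumed age effect of 0.1-0.4 log10.
5. Log any remaining departures in Appendix 2.

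The cost is SAP wording. No new data are needed, and age group is already recorded. Separately, the Groups 9-10 schedule of activities shows no humoral sample at Day 29, while Protocol Table 6 calls that visit safety and immunogenicity. The two need reconciling before the groups in the D28 post-vaccination-1 model are fixed.
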